3.2. Research Questions, study population

Research Questions

We aim to investigate the effect of TMS in various configurations on psychomotor retardation in patients diagnosed with MDD or schizophrenia. Diagnoses will be given following application of Mini-International Neuropsychiatric Interview (MINI)(Sheehan et al., 1998) and review of the complete cases files. The study consists of a single site four arm randomized, sham-controlled trial. In total, 80 patients will be randomly assigned to four groups (20 patients per group) receiving sessions of TMS of different stimulation parameters. Sham stimulation will be administered in one group. Regardless of the type and the frequency of TMS, the

stimulation protocol will consist of 15 daily sessions during a 3 week period. The four different stimulation conditions have been described above.

Outcome will be evaluated as improvement in gross motor behavior (actigraphy, SRRS), fine motor function (finger tapping test), and hand gesture performance (TULIA). In addition, changes may be demonstrated by the Hamilton Rating Scale for Depression (HAMD) (Hamilton, 1960), Montgomery Åsberg Depression Rating Scale (MADRS) (Montgomery and Asberg, 1979) Beck Depression Inventory (BDI) (Beck et al., 1961), Positive and Negative Syndrome Scales (PANSS) (Kay et al., 1987) and Scales for the Assessment of Negative Symptoms (SANS) (Andreasen, 1983), Clinical Assessment Interview for Negative Symptoms (CAINS) (Kring et al., 2013) and Bush Francis Catatonia Rating Scales (Bush et al., 1996). Clinical ratings will be assessed at baseline and after the last TMS session by a rater blinded to stimulation protocol. Statistical analysis will comprise ANOVAs of motor variables and stimulation mode as between subject variable. Clinical response will be defined as a 30% reduction of the SRRS scores. Frequency of response will be compared between groups using Chi²-Tests.

Study Population

80 in- and outpatients with schizophrenia or major depressive disorder according to DSM-5 displaying reduced levels of motor activity. Diagnoses will be given following application of MINI and review of the complete cases files.

Age: 18-65

Right-handed

Races: all ethnic groups

Gender: male and female. Pregnant patients will be eliminated.

Patients must have normal or corrected-to-normal vision and hearing.

3.3. Study Hypothesis

Psychomotor symptoms are frequent in schizophrenia and MDD. Various brain regions may contribute to psychomotor slowing, but the precise pathophysiology remains unclear. Patients will be randomly assigned to four groups receiving sessions of TMS in different configurations. After TMS sessions, patients are expected to display an improvement of fine and gross motor activity as well as gesture performance. Across diagnoses, patients with motor retardation will benefit from inhibitory stimulation over SMA. Furthermore, TMS of various stimulation parameters is expected to affect disorder specific symptoms e.g. depressive symptoms and negative symptoms, which will be rated before and after TMS.

4. Study design

4.1. Targeted primary end point and secondary end points (effectiveness and safety parameters)

Main objective is the effect of TMS on psychomotor retardation (PR) in patients with major depressive disorder or schizophrenia. Primary outcome marker will be the change in psychomotor performance as assessed by Salpêtrière Retardation Rating Scales (SRRS). Clinical response will be defined as a 30% reduction of the SRRS baseline scores.

Secondary targets will be the effect of TMS on other motor parameters and on specific symptoms e.g. depressive or negative symptoms.

Efficacy parameters: TMS parameters may be of critical role determining the effect of the applied TMS on motor symptoms.

Safety parameters: As specific safety factors in relation to TMS, patients with 1. past history of epilepsy, or 2. other increased neuronal activity in Electroencephalography (EEG), 3. MRI contraindications and 4. substance misuse will be excluded. EEG recordings will be held for all patients before the beginning of TMS. Patients will be screened every 5 sessions with SRRS and actigraphy. In case of moderate deterioration of motor performance (30% change of initial ratings of SRRS or/and actigraphy) or adverse reactions during the TMS protocol, patients will be excluded from further participation in the study. .

4.2. Specification of the parameter that is of primary interest and other parameters that will be assessed as additional, secondary end points.

Primary outcome of the study will be **efficacy** as defined by >30% improvement from the baseline score of the Salpêtrière Retardation Rating Scales (SRRS). Outcome will be further evaluated as improvement in gross motor behavior (actigraphy), fine motor function (finger tapping test), and hand gesture performance (TULIA). In addition, we will investigate the effect of TMS on the disorder specific symptoms. Patients will be assessed with the Hamilton Rating Scale for Depression (HAMD) (Hamilton, 1960), Montgomery Åsberg Depression Rating Scale (MADRS) (Montgomery and Asberg, 1979) Beck Depression Inventory (BDI) (Beck et al., 1961), Positive and Negative Syndrome Scales (PANSS) (Kay et al., 1987) and Scales for the Assessment of Negative Symptoms (SANS) (Andreasen, 1983), Clinical Assessment Interview for Negative Symptoms (CAINS) (Kring et al., 2013) and Bush Francis Catatonia Rating Scales (Bush et al., 1996). Clinical ratings will be assessed at baseline and after the last TMS **session** by a rater blinded to **stimulation protocol**. Statistical analysis will comprise ANOVAs of motor variables and stimulation mode as between subject variable. Clinical response will be defined as a 30% reduction of the SRRS scores. Frequency of response will be compared between groups using Chi²-Tests.

4.3 Study design, tabular overview, course of the study, study duration (for each participant), break-off criteria and procedure for unblinding

Study Design

Single site four arm randomized, sham-controlled trial to disentangle the **pathophysiology of psychomotor retardation**. We will investigate 80 in- and outpatients, aged between 18 and 65, diagnosed with MDD or schizophrenia,

displaying reduced levels of motor activity. Diagnoses will be given through application of MINI and review of the complete cases files. Only patients displaying reduced levels of motor activity assessed with Bern Psychopathology Scales (BPS) will be included and will be randomly assigned to four equal groups. Patients will be informed about the stimulation procedure and the goals of the study. Written informed consent will be obtained. Female patients will take a urine pregnancy test before the beginning of the TMS sessions and they will be required to use contraceptive methods during the TMS protocol in order to enroll in the study. In case of a suspicion of a pregnancy during the study despite the use of contraceptives a urine test will be taken. Subjects will undergo a series of diagnostic tests assessing primarily different psychomotor domains and secondarily disorder specific symptoms. Questions concerning demographic data (age, gender, education, occupational status) as well as substance use and medication will also be included. Each group will receive sessions of TMS of different stimulation parameters. Regardless of the type and the frequency of TMS, the stimulation protocol will consist of 15 daily sessions during a 3 week period. The four different stimulation conditions have been described above. Subjects will be reassessed after TMS.

Following assessments will be performed:

- Mini-International Neuropsychiatric Interview (MINI) – A validated structured diagnostic psychiatric interview.
- Bern Psychopathology Scales (BPS) – A validated quantitative and qualitative scales for the assessment of system-specific psychotic symptoms
- Actigraphy – gross motor activity levels will be recorded by wrist actigraphs
- Salpêtrière Retardation Rating Scales (SRRS) – A validated scales allowing the assessment various domains of psychomotor performance including gait, gross and facial motorics, speech and cognitive elements
- Finger tapping test – video-taped assessments of fine motor performance
- Test of Upper Limb Apraxia (TULIA) –video-taped, blinded ratings of gesture performance
- Patients with Major Depressive Disorder (MDD): Hamilton Rating Scale for Depression (HAMD), Montgomery Åsberg Depression Rating Scale (MADRS), Beck Depression Inventory (BDI) (Beck et al., 1961),
- Patients with Schizophrenia: Positive and Negative Syndrome Scales (PANSS), Scales for the Assessment of Negative Symptoms (SANS), Clinical Assessment Interview for Negative Symptoms (CAINS) and Bush Francis Catatonia Rating Scales (Bush et al., 1996).

Transcranial Magnetic Stimulation sessions

The first group will receive 15 Hz TMS over dorsolateral prefrontal cortex (DLPFC) repetitive TMS. As mentioned above, there is a considerable number of previous high frequency TMS trials at this site with significant effects on the psychomotor performance (Huber et al., 2003; Hausmann et al., 2004; Martis et al., 2003; Baeken et al., 2010). The rTMS protocol that will be used derives from the study of

Hernández-Ribas et al. (2013), which detected a significant antidepressant effect of high frequency TMS over DLPFC.

The second group will be **tested** with transcranial magnetic stimulation of 1 Hz rTMS over SMA/ pre- SMA. Low frequency TMS has been demonstrated to decrease motor cortex excitability, the motor consequences of which are still to be unraveled. Moreover, low frequency rTMS has shown a highly beneficial effect on motor symptoms in patients with Parkinson Disease (PD) (Shirota et al., 2013). We will use the stimulation protocol of the study of Shirota et al. (2013).

The third group will receive intermittent Thetaburst Stimulation (iTBS) 50 Hz over Supplementary Motor Area (SMA)/ Presupplementary Motor Area (pre-)SMA. iTBS is a modality of stimulation eliciting an excitatory effect on cortical excitability, applied primarily in patients with multiple sclerosis or post-stroke implications with beneficial findings. The findings of studies assessing the effect of iTBS over SMA on psychomotor performance in healthy individuals and patients with Parkinson Disease have been encouraging (Dusek et al., 2011; Ilic et al., 2012). We will apply the widely used protocol of the study of Huang et al. (2005).

The fourth group (control group) will receive sham stimulation over occipital cortex. In this group a placebo coil, similar to the real one will be used. According to the review of Loo et al. (2000) sham conditions including various coil positions have displayed a significant effect in many cases. Based on these findings, we chose to use a placebo coil over a different stimulation area expecting a negligible stimulation effect.

The complete stimulation details are given in section TMS Protocol. Regardless of the type and the frequency of TMS, the **stimulation** protocol will consist of 15 daily sessions during a 3 week period. The ratings mentioned above will be repeated after the end of the TMS.

Tabular overview

Selection of participants	Information about the procedure and the goals of the study
	Written informed consent is obtained
	Specific safety parameters for TMS sessions will be assessed
	EEG Recordings
	Bern Psychopathology Scales (BPS) for the assessment of motor activity levels
	Mini-International Neuropsychiatric Interview (MINI)
Assessment before TMS	Actigraphy
	Salpêtrière Retardation Rating Scales (SRRS)
	Finger tapping test
	Test of Upper Limb Apraxia (TULIA)
Specific assessment: patients with Major Depressive Disorder	Hamilton Rating Scale for Depression (HAMD)

	Montgomery Åsberg Depression Rating Scale (MADRS)
	Beck Depression Inventory (BDI)
Specific assessment: patients with schizophrenia	Positive and Negative Syndrome Scales (PANSS)
	Scales for the Assessment of Negative Symptoms (SANS)
	Clinical Assessment Interview for Negative Symptoms (CAINS)
	Bush Francis Catatonia Rating Scales (BFCRS)
Transcranial magnetic stimulation	Randomized allocation to four equal groups
	15 daily sessions (3 week period)
Assessment after TMS	Repetition of the assessments taken place before TMS

Course of the study

The study will be started immediately after ethical approval. Subject recruitment, testing and data analysis will last approximately 36 months.

The study will encompass the following periods:

Preparation (2 months)

At this period, the rater will be trained using the rating scales and the assessment methods. Additionally, the various departments of the clinic will receive detailed information on the study, while the function of all technical equipment and its' response to the design of the study will be tested. Modifications, if necessary, will be made.

Subject recruitment, ratings, TMS sessions and repetition of ratings (24 months)

During this phase, patients will be motivated to participate in the study. As the recruitment and screening of individuals will be taking place, TMS will be performed continuously during this period. Patients will be reassessed after every 5 sessions and in the end of the TMS. Contemporaneously, the data of the rating scales and methods will be digitalised and prepared for statistical analyses.

Analyses and publication (10 months)

After collecting all data, the final analyses will follow and manuscripts will be written.

Settings

Recruitment, screening and selection of patients will take place at the University Hospital of Psychiatry in Bern. The assessments and the TMS sessions will be carried

out at the Lab of the Department of Psychiatric Neurophysiology, University Hospital of Psychiatry in Bern.

Study duration for each participant

In total the duration for each participant will be as following

Duration of assessments

A) Pre TMS clinical ratings & tests	210 min
B) TMS sessions	30 min x 15 sessions=450 min
C) Post- TMS clinical ratings & tests	210 min

Procedure of unblinding

Reassessments after TMS sessions will be carried out by a rater, blinded to the **stimulation** allocation. The data of patients such as the TMS configuration delivered will be concealed in a sealed and opaque envelope and kept by the main investigator. The envelope will be opened only in case of adverse reactions, leading to discontinuation of the **rTMS sessions** and exclusion from the study.

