6.1. Effectiveness parameters: measuring methods and reference dates

The efficacy of TMS sessions will be evaluated primarily as improvement in SRRS baseline score after treatment. Furthermore, we investigate the effect of TMS on gross motor behavior (SRRS, actigraphy), fine motor function (finger tapping test), and hand gesture performance (TULIA). To this purpose, clinical ratings will be assessed twice, at baseline and after the last TMS **session**. Furthermore, changes may be demonstrated by the scales assessing the disorder specific symptoms; in patients with major depressive disorder, HAMD, MADRS and BDI, in patients with schizophrenia PANSS, SANS, CAINS and the Bush Francis Catatonia Rating Scales. Statistical analysis will comprise repeated measures ANOVAs of motor variables and stimulation mode as between subject variable. Clinical response will be defined as a 30% reduction of the SRRS scores.

7. Assessment of safety

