8.1. Definition of the primary end point and secondary end points

Primary outcome of the study will be clinical response as defined by >30% improvement from the baseline score of the Salpêtrière Retardation Rating Scales (SRRS). Moreover, gross motor behavior (actigraphy), fine motor function (finger tapping test), and hand gesture performance (TULIA) will be assessed at baseline and after the last TMS. Furthermore, we will investigate the efficacy of TMS on disorder specific symptoms; in patients with major depressive disorder, HAMD, MADRS and BDI, in patients with schizophrenia PANSS, SANS, CAINS and the Bush Francis Catatonia Rating Scales will be carried out before and after TMS. Statistical analysis will comprise ANOVAs of motor variables and stimulation mode as between subject variable. Clinical response will be defined as a 30% reduction of the SRRS scores. Frequency of response will be compared between groups using Chi²-Tests.

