8.3. Description of the statistical methods foreseen and the planned intermediate assessments

Descriptive data analyses will be performed using Statistical Package for Social Sciences SPSS 17.0® (SPSS Inc., Chicago, IL, USA). In order to compare efficacy of the intervention arms, the primary outcome will be the frequency of patients

achieving response to psychomotor retardation (i.e. >30% improvement from SRRS baseline scores). This group statistic will be calculated using Chi²-Tests.

In order to investigate the effect of rTMS on the psychomotor performance of participants, we will analyze changes in motor variables within and between groups using repeated measures-ANOVAs. This way, we will test for time effects and effects of stimulation protocol. In case of unequal distribution of descriptive parameters between groups, these parameters will be entered as covariates to the repeated measures ANCOVA. Before performing ANOVAs, a normalizing transformation will be carried out if necessary.

The same procedure will be followed in case of the diagnose specific symptoms ratings (BDI, MADRS, Hamilton, PANSS, SANS, CAINS).

To control if a possible improvement of psychomotor performance after rTMS may be attributed to a general clinical response, we will use the analysis of covariance (ANCOVA) with psychomotor performance ratings (before and after TMS) as within subjects factor and changes in ratings of diagnose specific symptoms ratings as covariate.

At three major recruitment steps (25% of total sample, 50% and 75% respectively) we will calculate the primary analysis. If one group proves to have significantly poorer outcome than the others, we will stop this study arm.

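### The primary outcome is worded as change in SRRS score in 4.1 and 6.1 but as >30% SRRS response in 4.2, 8.1 and 8.3, and nothing says which wording governs.

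*Combined protocol and SAP*

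**What the plan says.** Two descriptions of the primary outcome stand side by side.

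- **Change in score.** Section 4.1: "Primary outcome marker will be the change in psychomotor performance", measured on the SRRS. The next sentence defines clinical response but does not call it primary. Section 6.1: "The efficacy of TMS sessions will be evaluated primarily as improvement in SRRS baseline score after treatment". The analysis given there is "Statistical analysis will comprise repeated measures ANOVAs of motor variables and stimulation mode as between subject variable". Section 6.1 closes with the response definition but mentions no Chi² test.
- **Response.** Section 4.2 defines efficacy, as the primary outcome, by more than 30% SRRS improvement. Section 8.1: "Primary outcome of the study will be clinical response as defined by >30% improvement from the baseline score". In 8.3, "the primary outcome will be the frequency of patients" who reach that response, compared by Chi². Section 8.2 bases the sample size on a Chi² test of responders.

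Section 8.3 puts the repeated measures ANOVAs of motor variables in a separate paragraph and does not call them primary. Section 8.4 sets p<0.05 and gives no hierarchy or multiplicity rule.

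The cut-off also varies. Sections 4.2 and 8.1 each give both more than 30% and the form "Clinical response will be defined as a 30% reduction of the SRRS scores". Sections 3.2, 4.1 and 6.1 use only the latter form, and 8.3 uses only more than 30%.

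**The concern.** A protocol has to fix one primary outcome before anyone sees data. Here a reader could cite 4.1 or 6.1 for the continuous score, or 4.2, 8.1 or 8.3 for response, and either would look pre-specified. The two measures come from the same SRRS ratings but can give different answers, because one uses the whole change and the other only whether it crosses a threshold. A choice made after the data are known raises the false-positive rate above the nominal 5% and can decide whether the trial is called positive.

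The cut-off is a smaller ambiguity of the same kind. A fall from 20 to 14 is (20 − 14)/20 = 30% exactly: a responder under one wording and not under the other.

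**Working it through.** **1. Which outcome the sample size serves.** Inputs from 8.2: responders shared 25/25/40/10% against 25% in each arm, α = 0.05, power 0.90, df = 3.

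- w² = Σ(p − 0.25)²/0.25 = (0 + 0 + 0.0225 + 0.0225)/0.25 = 0.18, so w = 0.424.
- The critical Chi² value is 7.815. At N = 79, λ = 79 × 0.18 = 14.22 and power is 90.1%.

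The plan's 79, its λ of 14.22 and its rounded w of 0.42 all reproduce. The figure belongs to a Chi² test of responders; no calculation supports SRRS change. Whether a calculation on shares of responders suits a comparison of response rates between arms is a separate question, not addressed here.

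**2. False-positive rate if the primary were chosen afterwards.** Two independent tests at 5% would give 1 − 0.95² = 9.75%, and the upper bound is 10%. The two tests share the same scores, so the rate is lower. I checked it by simulating 4 × 20 patients with equal arms.

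Assumptions, none from the documents: whole-number SRRS scores, mean 25, SD 7, pre-post correlation 0.5 to 0.7. The ANOVA is taken as one-way ANOVA on change, which equals the group-by-time test of a two-time-point repeated measures ANOVA.

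At least one of the two tests had p<0.05 in about 7 to 9% of trials across runs. A run of 20,000 trials per setting gave 8.2 to 8.4%, with the common mean reduction set at 0, 3, 6 or 9 points. A different model (fractional improvement with SD 0.3, baseline mean 25, SD 5) gave 8.0 to 8.4%. Each test alone stays near 5%.

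**3. How often the two measures disagree.** Same assumptions, with mean reductions of 3, 6, 6 and 9 points (response about 23, 40, 40 and 59% at correlation 0.5):

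| | Correlation 0.5 | Correlation 0.7 |
|---|---|---|
| Power, Chi² on response | 47–48% | 67% |
| Power, ANOVA on change | 58% | 81–83% |
| Power, ANCOVA adjusted for baseline | 72% | 88% |

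Chi² and ANOVA on change differ in significance in about 24 to 26% of trials. The 20,000-trial run gave 26.6% at correlation 0.5 (18.9% ANOVA only, 7.7% Chi² only) and 24.1% at 0.7 (20.0% and 4.1%).

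**4. The cut-off.** In these simulations 0.3 to 0.8% of patients fall exactly at 30%. That is 80 × 0.003 = 0.24 to 80 × 0.008 = 0.64 patients in the whole trial.

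**The case against.** The strongest reply is that the plan does have one primary outcome and that 4.1 and 6.1 are loosely worded. Sections 4.2 and 8.1, whose titles say they specify the primary parameter, both name response; 8.3 gives it a test and 8.2 sizes the trial on it. The response definition that follows directly in 4.1 can be read as making the change operational. The ANOVA sentence in 6.1 covers motor variables collectively, and nearly the same sentence appears in 4.2 and 8.1, where response is plainly primary.

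Most of this stands. A reader might infer that the plan opens two primary tests at 5% each and so fails to control its error rate. The documents do not support that: no section declares co-primary outcomes or says that success on either suffices. The inflation arises only if the choice is made after the data are seen, against 8.1 to 8.3.

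A reader might also set the Chi² power of about 47% against 72% for a baseline-adjusted ANCOVA and conclude that the choice costs about 25 points. That ANCOVA is not the analysis 6.1 names. Against ANOVA on change the gap is about 10 to 11 points at correlation 0.5.

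What the reply does not remove is the text itself. Section 4.1 is also headed as the primary end point section, 6.1 ranks the score first, and nothing says which section prevails.

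**Conclusion.** The inconsistency is real and should be closed before data are examined. It is a failure to reconcile sections, not a design with two primary tests. Its potential size is a false-positive rate of about 7 to 9% instead of 5%, conditional on a post hoc choice, and conflicting conclusions in about a quarter of trials under the assumed effects. Both figures depend on the assumed SRRS distribution; the false-positive figure is the steadier, since two different models agree closely. The cut-off ambiguity is minor, touching under 1% of patients.

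**What to change.** - **Primary outcome.** Reword 4.1 and 6.1 so that response, tested by Chi², is the single primary outcome everywhere, as in 4.2, 8.1 and 8.3. Label SRRS change as a secondary outcome.
- **Cut-off.** Choose >30% or ≥30% and use it in 3.2, 4.1, 4.2, 6.1, 8.1 and 8.3.
- **Separate improvement.** In 8.3, analyse the secondary SRRS score by ANCOVA of the post-treatment score adjusted for baseline instead of repeated measures ANOVA. Under the assumptions above this raises power from about 58% to 72% at correlation 0.5, and from about 81% to 88% at 0.7.

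The first two items are wording only. The third changes a secondary analysis but needs no extra data. None alters the sample size or the primary test. No α split is needed: keeping both measures as co-equal primaries with a Bonferroni split would instead raise the plan's own N from 79 to 92, or leave 85% power at 80.
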